12.8 Populations for Analysis

Patients will be evaluable for response in the context of the Simon 2-stage methodology.

Safety analyses will be performed on the safety population, defined as all patients who receive any amount of study drug.

The evaluation of drug-specific toxicity will be based on data from patients who receive 1 dose of ACY-1215.

12.9 Analysis Schedule

12.9.1 Interim Analysis

12.9.1.1 Phase Ib

Upon enrollment of three patients into Arm A and then after a safety assessment has occurred,

Arm B, no additional patients will be accrued until completion of cycle one to adequately evaluate for dose limiting toxicities. Following determination of <1/3 of patients experiencing a DLT 3 additional patients will be enrolled for a total of 6 patients per Arm. If < 1/3 or < 2/6 patients experience a DLT, planned accrual will expand to a maximum of 10 patients in each arm. The Phase II study will not begin until all 10 patients have completed one full cycle of therapy.

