5.1.2 Regimen Description and Guidelines for Drug Administration

Treatment will be administered on an outpatient basis. All patients will take the oral ACY-1215 160mg for 28 consecutive days on a 28-day treatment cycle. Frequency in phase II will be determined based on Phase Ib results. ACY-1215 will be supplied as a liquid for oral administration (PO). Each dose will be administered at least 1 hour after ingestion of food and followed by at least 4 ounces of water. Patients will be instructed not to ingest food or other oral medication for at least 2 hours after each ACY-1215 dose. Reported adverse events and potential risks for oral ACY-1215 are described in Section 7. Appropriate dose modifications are described in Section 6. No investigational or commercial agents or therapies other than those described may be administered with the intent to treat the patient's malignancy.

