5.1.4 Dose-Limiting Toxicity

A dose limiting toxicity (DLT) is defined as any toxicity not specifically included in section 5.1.4 that occurs within cycle 1. DLT is also defined as any toxicity, occurring up to 7 days after completion of cycle 1 that results in a delay of initiating cycle 2. For patients who discontinue study drug administration after Cycle 1, DLT will be defined as any toxicity not specifically included in section 5.1.4 that occurs within 30 days of the last dose of drug on study, in cycle 1 that is not related to disease progression.

DLTs include:

Hematologic dose-limiting toxicity will be defined as either Grade 4 neutropenia that does not resolve to \leq Grade 2 within \leq 7 days, any Grade 4 thrombocytopenia, or any Grade 5 hematologic toxicity. At least three patients in each cohort must be evaluable for hematologic toxicity.

Non-hematologic dose-limiting toxicity will be defined as any Grade 3, 4 or 5 non-hematologic toxicity, with the exception of:

- Grade 3 nausea or Grade 3 vomiting that occurs in the setting of inadequate compliance with supportive care measures specified in Section 5.1.7 and lasts for less than 48 hours.
- Grade 3 diarrhea that occurs in the setting of inadequate compliance with supportive care measures specified in Section 5.1.7 and lasts for less than 48 hours.
- Grade 3 dehydration that occurs in the setting of inadequate compliance with supportive care measures specified in Section 5.1.7 and lasts for less than 48 hours.
- Grade 3 acidosis or alkalosis that responds to medical intervention by returning to \leq Grade 2 within 48 hours.
- Isolated (i.e. no other abnormalities) Grade 3 elevation of liver function tests (LFTs) without associated clinical symptoms, lasting for \leq 5 days in duration.
- Isolated (i.e. no other abnormalities) Grade 3 elevation of amylase without associated clinical symptoms, lasting \leq 5 days
- Grade 3 hypocalcemia, hypokalemia, hypomagnesemia, hyponatremia, or hypophosphatemia that responds to medical intervention.

- Grade 3 hypercholesterolemia.
- Grade 3 hypertriglyceridemia
- Grade 2 Alopecia
- Grade 3 Constipation
- Grade 3 Fatigue

Management and dose modifications associated with the above adverse events are outlined in Section 6.3.

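### Phase Ib accrual can resume, and Phase II can open, at completion of cycle 1, although the DLT definition can run past that point for patients whose cycle 2 is delayed or who stop drug

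*Combined protocol and SAP*

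**What the plan says.** **Release points.** Section 12.9.1.1 (Interim Analysis, Phase Ib) says that after three patients are enrolled in an arm "no additional patients will be accrued until completion of cycle one to adequately evaluate for dose limiting toxicities". Three more patients follow once fewer than one third are determined to have had a DLT, and accrual then expands to at most 10 per arm. It adds: "The Phase II study will not begin until all 10 patients have completed one full cycle of therapy". Arm B opens after a safety assessment of Arm A, for which no time is given (Synopsis, Treatment Plan; Sections 2.3, 5.1.1 and 12.1.1).

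**Cycle length.** The Regimen Description gives ACY-1215 "for 28 consecutive days on a 28-day treatment cycle".

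**DLT definition.** Section 5.1.4 has three limbs:
- "any toxicity not specifically included in section 5.1.4 that occurs within cycle 1";
- "any toxicity, occurring up to 7 days after completion of cycle 1 that results in a delay of initiating cycle 2";
- for patients who discontinue after cycle 1, toxicity "within 30 days of the last dose of drug on study, in cycle 1 that is not related to disease progression".

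**Limits.** The Synopsis and Sections 2.3, 5.1.1 and 12.1.1 allow expansion with up to 1 DLT in 3 and up to 2 in 6. Section 12.9.1.1 prints strict inequalities: below 1/3 and below 2/6. Section 12.3.1.1 stops enrolment into a cohort if DLTs exceed 1/3 or 2/6, with no time limit.

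**The concern.** Section 12.9.1.1 treats completion of cycle 1 as enough to evaluate DLTs. Two of the three limbs in Section 5.1.4 can produce a DLT after that. A delay to cycle 2 cannot be established on the last day of cycle 1. A toxicity in the weeks after a patient's last dose may not yet have occurred.

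The count at the decision can be too low but never too high, so any error favours expansion. The schedule makes this relevant. Dosing is continuous for 28 days, whereas the earlier myeloma study dosed on days 1-5 and 8-12 of 21 (Section 2.3). Planned cycle 1 evaluations stop at Day 15, and the criteria for starting a cycle are checked before each cycle begins. Toxicity from the second half of cycle 1 may therefore first be documented when cycle 2 is due. The decisions affected are the 3-to-6 and 6-to-10 expansions, the move to Arm B, and the choice of schedule for a 60-patient Phase II.

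**Working it through.** **1. Calendar check.** The inputs are the 28-day cycle (Regimen Description), the 7-day and 30-day limbs (Section 5.1.4) and the release at completion of cycle 1 (Section 12.9.1.1). Cycle 1 is assumed to run without interruption.

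| Patient | DLT window closes | Days past the Day 28 release |
|---|---|---|
| Starts cycle 2 on time | about Day 28 | essentially 0 |
| Cycle 2 delayed by toxicity | 28 + 7 = Day 35 | up to 7 |
| Stops drug, last dose Day 28 | 28 + 30 = Day 58 | 30 |
| Stops drug, last dose Day 14 | 14 + 30 = Day 44 | 16 |

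The unobserved share of the window at Day 28 is 7/35 = 20% in the second row and 30/58 = 52% in the third. These shares apply to those patients only.

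The last two rows depend on how the 30-day sentence is read. It concerns patients who stop after cycle 1, yet it also contains the phrase in cycle 1, which may locate the last dose or may confine the toxicity itself to cycle 1. On the second reading the 30-day extension disappears. The Day 14 row also needs the sentence to cover a patient who stops during cycle 1. Such a patient never completes the cycle, and the gates do not say how to handle that case.

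**2. Is the release tied to the window elsewhere?** No. The Synopsis and Sections 2.3, 5.1.1, 12.1.1 and 12.3.1.1 give no observation time. The pause in Section 12.9.1.1 is attached to the first three patients of each arm. The 6-to-10 step has no stated observation period.

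**3. Possible size.** The protocol states no passing probability to reproduce and gives no DLT rates, so the rates here are assumptions. Let the in-cycle DLT rate be 0.20. Let a further 0.10 or 0.20 of the remaining patients have a late DLT. The combined rates are 1 − 0.8 × 0.9 = 0.28 and 1 − 0.8 × 0.8 = 0.36.

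With at most 1/3 and then at most 2/6 (Section 12.1.1):

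P(pass) = P(0 of 3) × P(≤2 of next 3) + P(1 of 3) × P(≤1 of next 3)

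- p = 0.20: 0.512 × 0.992 + 0.384 × 0.896 = 0.852
- p = 0.28: 0.373 × 0.978 + 0.435 × 0.809 = 0.717
- p = 0.36: 0.262 × 0.953 + 0.442 × 0.705 = 0.562

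With below 1/3 and then below 2/6 (Section 12.9.1.1), that is 0 of 3 and then at most 1 of 6:

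P(pass) = P(0 of 3) × P(≤1 of next 3)

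- p = 0.20: 0.512 × 0.896 = 0.46
- p = 0.28: 0.373 × 0.809 = 0.30
- p = 0.36: 0.262 × 0.705 = 0.18

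In each set the first value is the decision read at Day 28, and the other two count every DLT. The comparison assumes that every late DLT is missed at the decision and has no later effect. It also gives every patient without an in-cycle DLT the same late risk, although only a patient who is delayed or stops can contribute one.

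**The case against.** The strongest reply is that the gates are minimum conditions. Completing cycle 1 is necessary, but expansion also follows a determination of the DLT fraction, and Arm B follows a safety assessment. A careful team would apply the Section 5.1.4 definition and wait. This stands in part: the text permits an early decision but does not direct one. A reader might infer that late DLTs are scored as absent, and the documents do not say that. Equally, nothing requires the wait, and Section 12.9.1.1 presents cycle 1 as adequate.

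Section 12.3.1.1 stops enrolment once the limit is exceeded, with no Day 28 cut-off. A late DLT could therefore halt a cohort already expanding. That is a partial offset, since patients enrolled in the meantime have been exposed.

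A reader might also infer that 20% of the window is lost for every continuing patient, or that Day 58 is settled. Neither holds: the 7-day limb needs a delay to cycle 2, and the 30-day sentence is ambiguous.

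No DLT fraction at 10 patients governs the opening of Phase II. Dose and schedule follow from the sponsor's and investigators' analysis of safety data, so the Phase II gate is the weaker part of the point.

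The earlier monotherapy data (15 myeloma patients) show no DLTs and no discontinuations for adverse events (Sections 7.3.3 and 7.3.4). They come from a different schedule and do not settle the rate here, but they do not support the assumed rates either.

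Finally, this version is labelled Amendment 3 Ph II, so Phase Ib accrual may be over. The documents do not say.

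**Conclusion.** The inconsistency is real and rests on the protocol's own dates. The release points can be met up to 7 days before the DLT window closes for a patient whose cycle 2 is delayed by toxicity. On one reading of the 30-day sentence, they can be met up to 30 days before it closes for a patient who stops drug. The gap is essentially zero for a patient who starts cycle 2 on time. Any resulting error makes a schedule look safer.

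The size cannot be derived from the documents. The differences in passing probability (0.85 against 0.72 or 0.56; about 0.46 against 0.30 or 0.18) illustrate direction and possible scale under assumed rates. They are not estimates for this trial. Moving from one set of printed limits to the other shifts the result more than the late DLTs do, so the conflict between Section 12.9.1.1 and the other sections needs resolving as well.

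**What to change.** - Reconcile Sections 5.1.4 and 12.9.1.1 so that the release point and the DLT window close together. This should cover the 3-to-6 step, the 6-to-10 step, the opening of Phase II and the safety assessment before Arm B. Which passage changes is for the protocol team.
- Clarify the 30-day sentence: whom it covers, and whether the cycle 1 phrase limits the last dose or the toxicity. State how a patient who stops during cycle 1 counts towards each gate.
- Reconcile the expansion limits in Section 12.9.1.1 with those in the Synopsis and Sections 2.3, 5.1.1 and 12.1.1.
- If Phase Ib accrual is already complete, state the observation window behind each reported DLT count, and confirm that the schedule choice used complete windows.

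The cost is protocol wording. If Phase Ib is still accruing and the decisions are timed to the longer window, it adds about one week per affected decision, and up to about 30 days when a patient has stopped drug.

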12.9.1.2 Phase II

Interim analysis will be performed following accrual of the first 22 patients to ensure a response rate of at least 10% to proceed to stage 2 of accrual. An early stopping rule will be in effect if <10% of patients achieve a response. If >10% achieve a response, Stage 2 will proceed.

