This is a phase II, single-arm, multicenter, open-label study in patients with relapsed or relapsed/refractory lymphoma. Utilizing the Simon 2 Stage Minimax design, an estimated 40 patients will be needed to determine efficacy at a power of 0.80 and type I error of 0.05. Using this design, there will be an early stopping rule if $< 10\%$ achieve a response in Stage 1. Twenty-two ($N=22$) patients will be accrued to Stage 1, of which 2 patients are required to achieve a response to allow accrual to Stage 2. Patients accrued to Stage 1 of the Phase II will be of all lymphoid malignancy subtypes including those with mantle cell lymphoma (MCL). Eighteen patients ($N=18$) will be treated in Stage 2, of which 8 responses would be needed to attain an efficacy of at about 25%. The safety, tolerability, single- and multiple-dose PK, pharmacodynamics, and anti-tumor activity of ACY-1215 also will be evaluated. Simultaneously in Stage 2, an additional cohort of 20 mantle cell lymphoma patients will be assessed to evaluate for a signal of efficacy in this subtype. These patients will be enrolled in parallel to the phase II study. Assuming success in Stage I, enrollment to Stage 2, and expansion of MCL cohort, the total number of patients will be 60 (Stage 1 $N=22$, Stage 2 $N=18$, MCL focused Expansion Phase $N=20$).

5.1.3 Treatment plan common to both Phase Ib and Phase II:

After executing written informed consent, patients will be evaluated for study eligibility during the Screening period within the Screening period before Cycle 1, Day 1 [C1D1]. Patients determined to be eligible will be treated on study. Patients will be evaluated on Days 1, 8, and 15 of Cycle 1.

On study drug administration days that coincide with scheduled study center visits, ACY-1215 will be administered at the study center.

- One cycle of therapy is comprised of 28 or 56 doses of ACY-1215.
- Administration of the study drugs will be allowed within 48 hours of the scheduled dates.
- Missed doses will not be made up.

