12.1 Statistical Methods

12.1.1 Phase Ib:

The study will follow the similar principles of a standard 3+3 dose escalation study in which less than one third of patients enrolled to a particular Arm must not have a dose limiting toxicity to allow for expansion. Three patients will be sequentially enrolled in one of two cohorts: Arm A and then after a safety assessment has occurred, Arm B for a total of six patients (3 in each arm). If $\leq 33\%$ of patients ($N \leq 1$) experiences a dose limiting toxicity (DLT) in a cohort, the cohort will be expanded to 6 patients. If there are $\leq 33\%$ ($N \leq 2$ DLTs), the cohort will be further expanded to a total of 10 patients (3+3+4). The total number of patients for both Arms A and B with full expansions will total of 20. If more than 1/3 or 2/6 patients experience a DLT, there will be no expansion. Safety data obtained from this Phase Ib will be analyzed by the sponsor and collaborating investigators to recommend a Phase II dose.

12.1.2 Phase II:

The study will employ the minimax Simon 2-stage design. In Stage 1, 22 patients will be enrolled. If < 2 patients experience an objective tumor response (defined as CR, or PR, as outlined by the 2007 International Harmonization Project criteria), the study will be discontinued. If 2 or more of the first 22 patients experiences CR, or PR, additional 18 patients will be enrolled in Stage 2. Enrollment into Stage 2 will begin only after least 2 objective response have been observed in Stage 1. (Enrollment into Stage 2 need not be delayed until the response status of all 22 Stage 1 patients is known.) The design parameters are as follows:

- 0.15: unacceptable response rate.

- 0.25: target response rate.
- $\alpha = 0.05$: the probability of declaring the drug effective when the true response probability is less or equal to 0.15.
- $\beta = 0.20$: the probability of declaring the drug as not effective when its true response probability is as large or larger than the target response rate 0.30.

Once enrollment begins for stage 2 of the study, an additional 20 patients will be enrolled per lymphoma subtype, specifically Mantle Cell Lymphoma. Therefore the total number of patients estimated to be enrolled is 60.

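### At exactly 2 responses in the 22 Stage 1 patients (9.1%), the count rule opens Stage 2 and the 10% rule stops the trial; nothing says which governs

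*Combined protocol and SAP*

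**What the plan says.** **Count rule.** Section 12.1.2 gives both sides. It stops the study "If < 2 patients experience an objective tumor response", and on the other side: "If 2 or more of the first 22 patients experiences CR, or PR, additional 18 patients will be enrolled in Stage 2". Section 5.1.2 (Phase II) has 22 patients in Stage 1, "of which 2 patients are required to achieve a response to allow accrual to Stage 2". The Sample Size part of the synopsis sets the same requirement of 2.

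**Percentage rule.** Section 12.9.1.2 describes the interim analysis after 22 patients as being there "to ensure a response rate of at least 10% to proceed to stage 2 of accrual". It adds: "An early stopping rule will be in effect if <10% of patients achieve a response". It then lets Stage 2 proceed above 10%. Section 5.1.2 also states it: "Using this design, there will be an early stopping rule if" fewer than 10% respond in Stage 1. That paragraph therefore carries both rules.

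**Timing.** Section 12.1.2 says "Enrollment into Stage 2 will begin only after least 2 objective response have been observed in Stage 1", and also "Enrollment into Stage 2 need not be delayed until the response status of all 22 Stage 1 patients is known". The 20-patient mantle cell lymphoma (MCL) cohort opens when Stage 2 enrolment begins.

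**Precedence.** None is given. Section 11.2 gives the DSMB oversight of interim analyses as laid down in the data analysis plan. Section 12.11 promises a formal statistical plan, due only before database lock. Section 12.8 refers to evaluability within the Simon design and goes no further.

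**The concern.** This is the only formal futility decision in Phase II, and it also releases the MCL cohort. If Stage 1 ends with exactly 2 responders, one section tells the investigators to continue and another tells them to stop. The boundary would then be chosen after the result is known, which a pre-specified rule is meant to prevent.

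The early-opening provision makes the conflict more likely to matter in practice. Stage 2 and the MCL cohort may start as soon as the second response is documented. Stage 1 can then finish at 2 of 22, and Section 12.9.1.2 would call for stopping a stage that is already enrolling.

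**Working it through.** **Inputs.** Stage 1 n = 22, Stage 2 n = 18, total 40, type I error 0.05, power 0.80 (Sections 5.1.2 and 12.1.2). Stated unacceptable rate 0.15 and target rate 0.25 (Section 12.1.2). Final threshold 8 responses, read here as 8 or more of 40 in total (assumption). The rate 0.10 is not in the plan; it is shown as a weaker-drug case and because it bears on where the design came from.

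**1. The plan's own design.** An exhaustive search for the Simon minimax design at type I error 0.05 and power 0.80 gives:

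| Unacceptable / target rate | Stop at Stage 1 if | Drug rejected if | Type I error | Power |
|---|---|---|---|---|
| 0.15 / 0.25 (as stated) | ≤ 8 of 55 | ≤ 20 of 97 | 0.049 | 0.801 |
| 0.10 / 0.25 (not stated) | ≤ 2 of 22 | ≤ 7 of 40 | 0.040 | 0.803 |

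The plan's 22, 40 and 8 do not follow from its stated rates. They do match 0.10 / 0.25, where 2 of 22 is the largest count that *stops* the trial. That suggests the count rule may be off by one, but it is an inference.

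**2. The two boundaries.** 10% of 22 is 2.2; 2/22 = 0.0909; 3/22 = 0.1364. The count rule stops at 0–1 and goes at 2 or more. The percentage rule stops at 0–2 and goes at 3 or more. They differ only at 2.

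**3. Chance of the disputed count, and of early stopping.** P(X = 2) = C(22,2) p²(1 − p)²⁰. Early stopping is P(X ≤ 1) under the count rule and P(X ≤ 2) under the percentage rule.

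| True rate p | P(X = 2) | Stop early, 2 needed | Stop early, 3 needed |
|---|---|---|---|
| 0.10 | 0.281 | 0.339 | 0.620 |
| 0.15 | 0.201 | 0.137 | 0.338 |
| 0.25 | 0.046 | 0.015 | 0.061 |

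**4. Expected size of the 40-patient part:** 22 + 18 × (1 − P(stop early)).

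- p = 0.15: 22 + 18 × 0.8633 = 37.5 with 2 needed; 22 + 18 × 0.6618 = 33.9 with 3 needed; difference 3.6.
- p = 0.10: 33.9 and 28.8; difference 5.1.
- p = 0.25: 39.7 and 38.9; difference 0.8.

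If the MCL cohort fills whenever Stage 2 opens (assumption), replace 18 by 38. The expected Phase II total is 54.8 against 47.1 at 0.15, and 47.1 against 36.4 at 0.10.

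**5. Stage 2 opened, but Stage 1 ends at exactly 2:** P(X = 2) / P(X ≥ 2).

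- p = 0.15: 0.2015 / 0.8633 = 0.23.
- p = 0.10: 0.2808 / 0.6608 = 0.42.
- p = 0.25: 0.0458 / 0.9851 = 0.05.

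**6. Effect on the final conclusion.** P(success) = Σ P(Bin(22,p) = x) × P(Bin(18,p) ≥ 8 − x), summed from the go boundary upwards.

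| True rate p | 2 needed | 3 needed | Difference |
|---|---|---|---|
| 0.10 | 0.0416 | 0.0398 | 0.0018 |
| 0.15 | 0.2427 | 0.2343 | 0.0084 |
| 0.25 | 0.8161 | 0.8032 | 0.0129 |

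At the stated unacceptable rate of 0.15 neither boundary holds type I error to 0.05. That comes from the design parameters and is a separate matter from this conflict.

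**The case against.** The count rule is the fuller statement. It sits in the statistical methods section with both sides and a trigger, and it is repeated in the synopsis and the treatment plan. Many readers would follow the integer and take 10% as a loose rounding of 2/22. That is a reasonable guess at intent, but Section 12.9.1.2 states the threshold with inequalities in both directions, and the minimax search points the other way. Frequency of mention does not settle it.

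The effect on the final efficacy conclusion is small, and only one Stage 1 count is affected. Both points stand. Even at 0.10 the disputed count is missed about 72% of the time (1 − 0.281). The case rests on exposure and on the integrity of the interim decision.

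The largest figures are at 0.10, a rate the plan does not state. That is fair, and the 0.15 figures should carry the argument.

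Section 5.1.2.2 requires a review of all first-stage safety data before Stage 2 and the expansion cohort enrol, which may limit early opening in practice. It does not address response, so it does not break the tie.

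The conflict assumes a denominator of 22. If un-evaluable patients were dropped without replacement, 2/20 would be exactly 10%. The count rule would then go, while Section 12.9.1.2 would be unclear in itself, since it asks for at least 10% in one sentence and more than 10% in another. This moves the ambiguity without removing it.

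**Conclusion.** The concern holds and must be fixed. With 22 patients in the denominator, the plan gives opposite instructions at exactly 2 responses and no order of precedence. At the stated unacceptable rate of 0.15 that outcome has probability 0.20, and the choice of boundary moves early stopping between 0.14 and 0.34. The contradiction itself is arithmetic and needs no assumption about response rates. The success probabilities assume 8 of 40 in total, and the Phase II totals assume the MCL cohort fills whenever Stage 2 opens. Which boundary was intended cannot be established from the documents.

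**What to change.** 1. State one integer boundary, worded identically in the synopsis, Section 5.1.2 (Phase II), Section 12.1.2 and Section 12.9.1.2, and delete every percentage version of the rule.
2. Use the same integer in the early-opening trigger in Section 12.1.2, which also releases the MCL cohort.
3. Choose the integer from the intended design. If that was 0.10 against 0.25, write: *Stop if 2 or fewer of the 22 Stage 1 patients respond; Stage 2 and the MCL cohort may open once 3 responses are documented.* If 2 was intended, keep the count rule and report its early-stopping probability (0.14 at 0.15, 0.34 at 0.10).
4. Advisable in the same amendment: define which 22 patients form the denominator, and whether patients censored and replaced under Sections 4.5 and 6.1 stay in it. The design rates, and the wording that seems to ask for 8 responses among the 18 Stage 2 patients, should be settled at the same time.

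**Cost.** This is a wording amendment in four places and leaves the maximum sample size unchanged. Choosing 3 lowers power at 0.25 from 0.816 to 0.803 and raises the chance of stopping a 25%-active drug at Stage 1 from 1.5% to 6.1%. Choosing 2 means 3.6 more expected patients in the 40-patient part at 0.15, and 5.1 more at 0.10, than choosing 3. The decision needs to be on record before Stage 1 responses are known.
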